9.2 SAMPLE SIZE DETERMINATION

The goal is to enroll up to 100 subjects; however, realistically, it may only be possible to enroll a smaller cohort. The ability to recruit for this study will depend on the rarity of such allergic reactions in the population and the acceptability of repeat vaccination and a 4-day hospital stay among individuals who have had these reactions. Current data indicates an extremely low systemic reaction rate, although it is likely that the overall rate may be higher since individuals recruited for this study have a history of a systemic allergic reaction following administration of the first dose of the vaccine. In sum, the study will provide more precise estimates with greater enrollment; however, even if fewer than 100 subjects enroll, the resulting data will provide valuable new information.

Since the primary goal of the study is estimation, we present the following example exact confidence intervals as a function of varying sample size and varying outcomes to illustrate achievable precision of estimates. We present such confidence intervals for the primary endpoint,

and also estimation of the risk difference of active vaccine versus placebo vaccine. The difference between active and placebo can be estimated in 2 different ways: one compares the results in the randomized arms at the first shot; and the other compares results within a subject across the 2 study vaccinations, exploiting the crossover design. Tables below present a subset of example scenarios in the study.

Table 5: Exact 95% Clopper Pearson Confidence Intervals for Primary Outcome, by Sample Size and Proportion with Systemic Allergic Reaction to Second Dose

Total N	Observed Reaction Rate					
	.00	.20	.40	.60	.80	1.00
5	0-0.522	0.005-0.716	0.053-0.853	0.147-0.947	0.284-0.995	0.478-1
10	0-0.308	0.025-0.556	0.122-0.738	0.262-0.878	0.444-0.975	0.692-1
15	0-0.218	0.043-0.481	0.163-0.677	0.323-0.837	0.519-0.957	0.782-1
20	0-0.168	0.057-0.437	0.191-0.639	0.361-0.809	0.563-0.943	0.832-1
40	0-0.088	0.091-0.356	0.249-0.567	0.433-0.751	0.644-0.909	0.912-1
60	0-0.06	0.108-0.323	0.276-0.535	0.465-0.724	0.677-0.892	0.94-1
80	0-0.045	0.119-0.304	0.292-0.516	0.484-0.708	0.696-0.881	0.955-1
100	0-0.036	0.127-0.292	0.303-0.503	0.497-0.697	0.708-0.873	0.964-1

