The examples above assume that if a subject reacts to the placebo phase, they will also react to the active vaccine phase. For example, with 10 subjects, and a reaction rate of 80% in the active vaccine and 20% in the placebo, this means that 2 subjects react to both active vaccine and placebo, 6 subjects react only to active vaccine, and 2 subjects react to neither. And, in this example the 95% confidence interval for excess reaction rate in active vaccine minus placebo is (.04, .878). The confidence intervals in this table are narrower than the ones in the previous table, since they use information from both study vaccinations. (There are other scenarios to get the same reaction rates [i.e. in the previous example, 1 subject reacts to both active vaccine and placebo, 7 subjects react only to active vaccine, 1 subject reacts only to placebo, and 1 subject reacts to neither], but these alternatives are not presented here, and the confidence intervals would be slightly different.)

While hypothesis testing will be done comparing active vaccine and placebo reactions, this goal is viewed as secondary to estimation of the difference.

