9.4 STATISTICAL ANALYSES

9.4.1 General Approach

Most analyses will result in estimates of binary endpoints and will be presented as proportions and corresponding exact 95% confidence intervals.

Exploratory endpoints, such as mechanistic endpoints, will be presented as means with standard deviations and/or as medians and interquartile ranges. Graphical presentation may be useful.

While hypothesis testing is likely to be limited in scope, two-sided p-values with alpha=.05 will be used, with appropriate cautions regarding interpretation due to multiplicity.

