9.4.3 Analysis of the Secondary Endpoint(s)

Analyses to simple single proportion estimates will follow the same approach described for the primary endpoint.

Analysis of risk difference between active and placebo vaccines will be addressed in 2 separate ways. First, using only data from the first study vaccination, the risk difference will be estimated (proportion with systemic reaction in the active vaccine arm minus the analogue in the placebo arm) with an unconditional exact confidence interval. The second approach will exploit the crossover design (i.e., comparing each individual's active vaccine to placebo response), by estimating the risk difference using a McNemar's approach to an exact confidence interval.[\[34\]](#) While the McNemar's approach should be more precise than the group comparison approach at the first study vaccination, the potential for missing data on the second study vaccination, especially in the initial vaccine arm is not ideal. If there are such missing data, the second study vaccination will be imputed in the most extreme ways (i.e., smallest risk difference and largest risk difference) to see if the results are robust.

Hypothesis testing can be done for the active vaccine versus placebo risk difference. A Fishers exact test will be done when comparing the randomized arm at the first study vaccination. An exact McNemar's test will be done when comparing the within-subject differences. Approaches to missing data for McNemar's follow the estimation approaches.

A signed rank test will also be done to compare severity of reaction at the first vaccine (i.e., done prior to enrollment) to active study vaccine (where the difference in grade is the metric). Since that analysis assumes grade is linear, these data will also be analyzed using a purely ordinal approach to grade using a longitudinal GEE model with a cumulative logit link; this is effectively a generalization of McNemar's test, but for ordinal instead of binary data. Tabular data will also be presented.

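### Section 9.2 understates how far the paired interval depends on the pairing, and its claim that Table 7 is narrower than Table 6 fails in the 1.00/.00 column

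*Combined protocol and SAP*

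**What the plan says.** Section 9.2 gives example intervals "to illustrate achievable precision of estimates" because enrolment may fall well short of 100. Table 6 compares the randomised arms at the first study vaccination. Table 7 compares each subject's active and placebo phases.

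The text after Table 7 makes three statements:

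- On the pairing: "The examples above assume that if a subject reacts to the placebo phase, they will also react to the active vaccine phase".
- On width: "The confidence intervals in this table are narrower than the ones in the previous table, since they use information from both study vaccinations".
- On other pairings with the same marginal rates, it names one for N=10 at .80/.20 ("1 subject reacts to both active vaccine and placebo, 7 subjects react only to active vaccine, 1 subject reacts only to placebo", and the remaining subject to neither) and then says "but these alternatives are not presented here, and the confidence intervals would be slightly different".

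Section 9.4.3 plans the within-subject analysis "by estimating the risk difference using a McNemar's approach to an exact confidence interval" and adds: "An exact McNemar's test will be done when comparing the within-subject differences". Section 9.4.1 sets the level: "two-sided p-values with alpha=.05 will be used".

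**The concern.** Table 7 shows only the pairing with no placebo-only reactors, which is the most precise one for given rates in the .80/.20 and .60/.20 columns. Placebo-only reactors are a foreseen outcome: Section 4.2 justifies the placebo on the ground that anxiety can mimic an allergic reaction. A reader told that other pairings hardly matter will take the printed limits as representative at the small sample sizes the section is written for.

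Whether zero is excluded matters on the plan's own terms. The worked example under Table 6 reads an interval that excludes zero as showing that the vaccine causes excess reactions.

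The width sentence can be checked against the two printed tables, and it fails in one column. That column also contains two Table 6 lower limits that fall as N rises, although the observed result is the same in every row.

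**Working it through.** **Inputs.** N=10 at .80/.20. Printed pairing: 2 both, 6 active-only, 0 placebo-only, 2 neither, interval 0.04 to 0.878. Named alternative: 1 both, 7 active-only, 1 placebo-only, 1 neither. All are from Section 9.2. The method is an exact matched-pair interval compatible with exact McNemar (Section 9.4.3, reference 34).

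**Exact McNemar p-values.** With x active-only, y placebo-only and m = x + y, the two-sided p is 2·P(Bin(m, ½) ≥ max(x, y)).

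- 6 vs 0: 2 × 1/64 = 0.031
- 7 vs 1: 2 × (8 + 1)/256 = 0.070
- 9 vs 1: 2 × (10 + 1)/1024 = 0.021
- 10 vs 2: 2 × (66 + 12 + 1)/4096 = 0.039
- 11 vs 3: 2 × (364 + 91 + 14 + 1)/16384 = 0.057

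**Paired interval.** Let θ be the probability of a discordant pair and β the probability that a discordant pair is active-only, so the risk difference is δ = θ(2β − 1). Take the Clopper-Pearson confidence distributions:

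- θ_L ~ Beta(m, N−m+1) and θ_U ~ Beta(m+1, N−m)
- β_L ~ Beta(x, y+1) and β_U ~ Beta(x+1, y)

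The lower limit is the 2.5% quantile of (2β_L − 1)θ, with θ_L where 2β_L − 1 > 0 and θ_U otherwise. The upper limit is the 97.5% quantile of (2β_U − 1)θ, with the roles of θ_L and θ_U exchanged. This reproduces all 24 printed Table 7 intervals to within 0.001, including 0.040 to 0.878 for 6 vs 0 at N=10.

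| N, rates | active-only vs placebo-only | 95% interval or lower limit | p |
|---|---|---|---|
| 10, .80/.20 | 6 vs 0 (printed) | 0.04 to 0.878 | 0.031 |
| 10, .80/.20 | 7 vs 1 (named in 9.2) | -0.043 to 0.915 | 0.070 |
| 15, .60/.20 | 6 vs 0 (printed) | 0.026 to 0.677 | 0.031 |
| 15, .60/.20 | 7 vs 1 | -0.029 to 0.708 | 0.070 |
| 20, .60/.20 | 8 vs 0 (printed) | lower 0.084 | 2/256 = 0.008 |
| 20, .60/.20 | 9 vs 1 | lower 0.048 | 0.021 |
| 20, .60/.20 | 10 vs 2 | lower 0.017 | 0.039 |
| 20, .60/.20 | 11 vs 3 | lower -0.011 | 0.057 |

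For the named alternative the width goes from 0.878 − 0.040 = 0.838 to 0.915 + 0.043 = 0.958, a ratio of 1.14.

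**Reach.** The .80/.20 and .60/.20 columns contain 13 intervals that exclude zero. Three can include it under another pairing: N=10 .80/.20, and N=15 and N=20 .60/.20. The other ten stay above zero even with the maximum number of placebo-only reactors. Their lower limits are then:

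- .80/.20: 0.036 (N=15), 0.120 (20), 0.280 (40), 0.347 (60), 0.386 (80), 0.412 (100)
- .60/.20: 0.102 (N=40), 0.162 (60), 0.197 (80), 0.221 (100)

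At larger N the effect of one placebo-only reactor is small: the .80/.20 width goes from 0.382 to 0.405 at N=40 and from 0.224 to 0.231 at N=100.

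**Width comparison, 1.00/.00 column.** Every upper limit is 1, so each width is 1 minus the printed lower limit.

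| N | Table 7 | Table 6 | Table 7 is |
|---|---|---|---|
| 10 | 1 − 0.338 = 0.662 | 1 − 0.383 = 0.617 | wider |
| 20 | 1 − 0.621 = 0.379 | 1 − 0.663 = 0.337 | wider |
| 40 | 1 − 0.797 = 0.203 | 1 − 0.824 = 0.176 | wider |
| 60 | 1 − 0.861 = 0.139 | 1 − 0.881 = 0.119 | wider |
| 80 | 1 − 0.895 = 0.105 | 1 − 0.702 = 0.298 | narrower |
| 100 | 1 − 0.915 = 0.085 | 1 − 0.597 = 0.403 | narrower |

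In the other two columns Table 7 is narrower in every shared row.

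**Table 6 at N=80 and 100.** With N/2 per arm, all vaccine recipients reacting and no placebo recipient reacting, the probability of that outcome at a true difference d is at most ((1+d)/2)^N. Setting this to 0.025 gives d = 2·0.025^(1/N) − 1.

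- N = 6, 10, 20, 40, 60: 0.0815, 0.3830, 0.6631, 0.8238, 0.8807. The printed values (0.082, 0.383, 0.663, 0.824, 0.881) agree within 0.001.
- N = 80, 100: 0.910 and 0.928. The printed values are 0.702 and 0.597, where the tail is (1.702/2)^80 = 2.5×10⁻⁶ and (1.597/2)^100 = 1.7×10⁻¹⁰ instead of 0.025.

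Against the recomputed limits, Table 7 is wider at N=80 (0.105 vs 0.090) and N=100 (0.085 vs 0.072) as well.

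**The case against.** The case for leaving the text alone has several parts.

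- The pairing assumption is disclosed, the counts of the alternative are printed, and no Table 7 cell is wrong. The limits move by 0.083 and 0.037 on an interval already 0.838 wide. Testing is secondary to estimation, and the final analysis uses the observed pairs. Section 4.1 reports that by September 15, 2022 only 2 participants had yet to complete the 5-month visit, so the illustration no longer steers enrolment. All of this stands and limits the importance of the point. It does not make the description right for the example it refers to.
- The width sentence follows a .80/.20 example and is true as printed in 14 of 18 shared cells, with the four failures between 0.020 and 0.045. That also stands, but the sentence carries no qualification.
- The paper behind the paired method is not available here. The reconstruction can be matched to printed cells only where there are no placebo-only reactors, and the grid and simulation checks use the same construction. So the exact limits for the alternative rest on it. The inclusion of zero does not, because an interval compatible with exact McNemar must include zero when p = 0.070.
- Other Table 6 cells may also need work. Ordering tables by the simple difference reproduces the .80/.20 lower limits at N=20 and 40, but at the printed limits for N=60, 80 and 100 the maximum tail is about 0.011, 0.007 and 0.005. Section 9.4.3 does not state the ordering, so no replacement values are offered. This argues for re-running those rows.

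**Conclusion.** Both statements are wrong as written. For the alternative named in Section 9.2, the interval becomes -0.043 to 0.915: about 14% wider, including zero, with p = 0.070 in place of 0.031. Describing the difference as slight is fair at N=40 and above but not at N of about 10 to 20, where 3 of the 13 zero-excluding intervals can lose that property. The width claim fails as printed in four cells of the 1.00/.00 column, and in six once the N=80 and N=100 lower limits of Table 6 are recomputed.

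The width comparison at N=10 to 60 needs only subtraction of printed limits, and the loss of zero exclusion needs only the exact McNemar p-value. The specific limits for other pairings assume the reconstructed method, which matches every printed Table 7 cell. The consequences are minor: the errors concern how precision is described, and the planned analysis is unaffected.

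**What to change.** 1. Print the interval for the named N=10 alternative, confirmed with the software used for Table 7 (recomputed here as -0.043 to 0.915).
2. Replace the remark on other pairings with a statement that the printed pairing is the most precise one in the .80/.20 and .60/.20 columns, and that at N of about 10 to 20 other pairings can bring zero into the interval.
3. Limit the width claim to those two columns under the printed pairing.
4. Correct the Table 6 1.00/.00 lower limits at N=80 and N=100 (0.910 and 0.928) before describing that column as the exception. Re-run the N=60, 80 and 100 rows of Table 6 at the same time and state the ordering used.

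A full table of ranges over pairings is optional. The cost is two sentences, one added interval, two corrected cells and a re-run of three table rows. The stated paired precision becomes less favourable at small N. Design, sample size and analysis method do not change.

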9.3 POPULATIONS FOR ANALYSES

The modified intention-to-treat analysis data set includes all subjects who receive the first injection in the study and are followed for the initial 3 hours for systemic allergic reaction.

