4. Investigate mental health characteristics of participants who experience an allergic reaction to the COVID-19 vaccine.
5. Assess psychological impact of allergic reactions to the COVID-19 vaccine and examine changes in stress levels over time.
6. Assess anxiety levels in participants and examine changes in anxiety over time.
7. Assess the proportion of participants who experience no reaction or only a mild reaction (CoFAR Grade 2 or below) to a booster dose of the Pfizer-BioNTech vaccine after previously demonstrating a systemic allergic reaction (CoFAR Grade 2 or 3 reaction regardless of tryptase OR Grade 1 reaction with elevated tryptase [1.2 X baseline plus 2 ng/mL]) to their first full dose of the Pfizer-BioNTech or Moderna COVID-19 vaccine and no allergic reaction or a mild reaction (CoFAR Grade 2 or below) to a subsequent (second) dose of the Pfizer-BioNTech vaccine.
8. Assess the development of autoantibodies after COVID-19 vaccination.

Endpoints:

Primary Endpoint:

1. The proportion of participants who previously demonstrated a systemic allergic reaction (CoFAR Grade 2 or 3 reaction regardless of tryptase OR Grade 1 reaction with elevated tryptase [1.2 X baseline plus 2ng/mL]) to their first full dose of the Pfizer-BioNTech or Moderna COVID-19 vaccine who experience a **systemic allergic reaction** (CoFAR Grade 2 and above reaction regardless of tryptase, or CoFAR grade 1 with elevated tryptase [1.2 X baseline plus 2ng/mL]) within the 3-hour post-vaccine observation period to a subsequent dose of the Pfizer-BioNTech vaccine.

Secondary Endpoints:

2. The proportion of participants who previously demonstrated a systemic allergic reaction (CoFAR Grade 2 or 3 reaction regardless of tryptase OR Grade 1 reaction with elevated tryptase [1.2 X baseline plus 2ng/mL]) to their first full dose of the Pfizer-BioNTech or Moderna COVID-19 vaccine who experience a **severe systemic allergic reaction** (CoFAR grade 3 reaction and above) within the 3-hour post-vaccine observation period to a subsequent dose of the Pfizer-BioNTech vaccine.

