6.3 MEASURES TO MINIMIZE BIAS: RANDOMIZATION AND BLINDING

Participants will be randomized to receive either Pfizer-BioNTech vaccine or placebo on Day 1 in a 1:1 ratio at enrollment via block randomization. On Day 2, subjects will receive whichever of vaccine or placebo that was not given on Day 1. A randomization scheme will be generated by the NIAID Biostatistics Research Branch who will provide a randomized list of arm assignments to the NIH Clinical Center Pharmacy. The randomization code list will be maintained by the Investigational Drug Control Unit (IDCU) in the electronic Investigational Drug Management System (IDMS).

The participants, the clinical staff, and the study team will be blinded to the order of study vaccine assignments. The unblinded pharmacy staff is responsible for maintaining security of the assignments.

Intentional unblinding: Unblinding will occur after the last participant has completed Visit 1. There will be no emergency unblinding for CoFAR Grade 3 or lower reactions because allergic and anaphylactic reactions to the vaccine are expected and will be treated per standard clinical care, and it is not necessary to unblind to do so. However, if a CoFAR Grade 4 or higher systemic allergic reaction or other life-threatening AE occurs, then both the investigator and the participant will be unblinded. If a CoFAR Grade 4 or higher reaction occurs on day 1, then the participant will not receive the study intervention the next day (either placebo or vaccine).

To break a treatment blind, the principal investigator will request a participant's treatment assignment from the IDCU. If an emergency request for treatment assignment is made by an individual other than the principal investigator and the principal investigator is not immediately available, the request will be made to one of the physician associate investigators, who will then contact the IDCU or appropriate NIH pharmacy after-hours contact to obtain the treatment assignment. If a participant's study agent assignment is unblinded, the information will be provided to only the individuals needing it for treatment decisions; all attempts will be made to maintain the blind of the study team.

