8.4.3.2 Replacement of Withdrawn Subjects or Subjects Who Discontinue Study Agent

Subjects who are withdrawn from the study or discontinue study vaccinations will not be replaced.

All subjects exposed to study agents must be included in the safety dataset.

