9.3.1 Evaluable for Toxicity

All participants will be evaluable for toxicity from the time of their first study vaccination.

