9.4.2 Analysis of the Primary Endpoints

The primary endpoint will be estimated using the proportion of reaction to the active vaccine, and presented with a 95% confidence interval, using the Clopper-Pearson method.

It is not anticipated that individuals randomized to receive placebo vaccination first will not get the active vaccine, but if this occurs, the following approaches will be used: i) analysis in the population with complete data (which will be the primary approach), and ii) analysis where missing data is imputed to be a vaccine reaction.

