9.4.4 Safety Analyses

The primary and secondary endpoints of this study are focused on safety and will be evaluated and analyzed as described above. Allergic reactions will be scored using the CoFAR Grading Scale for Systemic Allergic Reactions Version 3.0 and the Brighton Collaboration Criteria. Other

AEs following active vaccine administration are expected as described in Section 2.3.1, and will be assessed during the participant's ICU stay as well as the remote follow-up within 1 week post-discharge (Visit 2) and at the in-person follow-up visits (Visits 3, 4, and 6). Efforts will be made to record start and stop dates of all AEs (both allergic and nonallergic in nature), severity, relationship to the study intervention, and expectedness based on study intervention. If participants experience a CoFAR Grade 4 or higher reaction on Day 1, or any life-threatening adverse reaction related or unrelated to the study intervention, then no additional dosing will occur and participants will be followed per study protocol.

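### The analysis set in section 9.3 requires 3 hours of follow-up after the first injection, which can leave out an early reactor and, for placebo-first participants, is tied to the wrong dose.

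*Combined protocol and SAP*

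**What the plan says.** Section 9.3 gives one analysis set for the allergic-reaction outcomes. It "includes all subjects who receive the first injection in the study and are followed for the initial 3 hours for systemic allergic reaction". Two conditions must therefore be met: the first injection was given, and follow-up ran for 3 hours after it.

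The primary endpoint (section 1.1) is a systemic reaction "within the 3-hour post-vaccine observation period to a subsequent dose of the Pfizer-BioNTech vaccine", and section 9.4.2 states that "The primary endpoint will be estimated using the proportion of reaction to the active vaccine". The endpoint counts CoFAR Grade 2 and above, and Grade 5 in Appendix A is death.

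The order of injections is random. Section 6.3 says "Participants will be randomized to receive either Pfizer-BioNTech vaccine or placebo on Day 1 in a 1:1 ratio at enrollment via block randomization".

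Two other sections take a wider view of who is included. Section 8.4.3.2 says "All subjects exposed to study agents must be included in the safety dataset", and section 9.3.1 says "All participants will be evaluable for toxicity from the time of their first study vaccination". Section 9.4.4 adds that "The primary and secondary endpoints of this study are focused on safety".

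On missing data, section 9.4.2 begins "It is not anticipated that individuals randomized to receive placebo vaccination first will not get the active vaccine". If that does happen, it prescribes a complete-data analysis as primary and a second analysis that imputes a reaction. For the paired comparison, section 9.4.3 imputes a missing second vaccination at both extremes.

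**The concern.** There are two separate problems with the condition in 9.3.

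**It depends on what happens after dosing, and the outcome itself can cause it to fail.** A fatal reaction one hour after the active dose is a primary event by definition, yet that participant was not followed for 3 hours. The same holds for a vaccine-first participant who reacts and then withdraws inside the window, since section 7.2 allows withdrawal at any time. Nothing in 9.3 says that a reaction already observed secures entry to the set.

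**For placebo-first participants it is tied to the wrong injection.** Their follow-up is checked after saline. Section 9.3 sets no requirement for the 3 hours after the active dose, which is the window the primary endpoint uses. Section 9.4.2 fills only part of that gap: it covers an active dose that was never given, not one that was given and followed by a short observation period. The plan does not say how such a participant is scored.

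At stake is the numerator and denominator of the primary proportion, in a study that may enroll few people. Section 9 says no formal SAP is intended, so this section is where the rule has to be stated.

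**Working it through.** **Inputs**
- Analysis set: section 9.3. Endpoint and its window: section 1.1. Method: Clopper-Pearson 95% interval, section 9.4.2.
- Sample size: up to 100, possibly far fewer (section 9.2). Table 5 runs from N = 5 to N = 100.
- Assumption: exactly one participant has an incomplete window. The documents give no expected number, so the figures below show the effect of a single case and do not forecast one.

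**Formula.** For x events in n, the lower limit is the 0.025 quantile of Beta(x, n-x+1) and the upper limit is the 0.975 quantile of Beta(x+1, n-x). The lower limit is 0 when x = 0 and the upper limit is 1 when x = n.

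**Check against the plan.** This formula reproduces all 48 cells of Table 5 to the printed precision. For example, N = 20 at an observed rate of 0.20 (x = 4) gives 0.057-0.437, as printed.

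**One reactor excluded** (x and n both fall by 1), starting from an observed rate of 20%:

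| All exposed kept | 95% CI | Reactor excluded | 95% CI |
|---|---|---|---|
| 2/10 = 20% | 2.5-55.6% | 1/9 = 11.1% | 0.3-48.2% |
| 4/20 = 20% | 5.7-43.7% | 3/19 = 15.8% | 3.4-39.6% |
| 8/40 = 20% | 9.1-35.6% | 7/39 = 17.9% | 7.5-33.5% |
| 20/100 = 20% | 12.7-29.2% | 19/99 = 19.2% | 12.0-28.3% |

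If the excluded participant is the only reactor, 1/20 = 5% (0.1-24.9%) becomes 0/19 = 0% (0-17.6%). The report would then show no reactions although one was seen.

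**One non-reactor excluded** (only n falls): 4/20 = 20% becomes 4/19 = 21.1% (6.1-45.6%). The filter can therefore move the estimate in either direction.

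**The remedy on the same scale.** Take 20 participants given the active dose, 4 with a reaction, and one of the other 16 with a short window. Scored as a non-reactor the result is 4/20 = 20% (5.7-43.7%). Scored as a reactor it is 5/20 = 25% (8.7-49.1%). Reporting both shows how far that one participant can move the result.

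**Why short windows without a reaction should not go to the complete-data rule.** If early-ending participants with a reaction are counted and those without one are removed, an incomplete window enters the estimate only when it contains an event. In the same example the result would be 4/19 rather than 4/20. That biases the proportion upward and shrinks the denominator.

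**The case against.** The strongest reply is that the situation hardly arises. Injections are given in the ICU with at least 3 hours of monitoring (section 1.3, footnote h). Reactors are treated and monitored there (section 4.1). A participant whose dosing stops is still followed (sections 8.4.5 and 9.4.4). A reader might infer from 9.3 that a reaction ends observation and so removes the reactor. The documents do not support that: it would take death or withdrawal within 3 hours. A death would also halt the study (section 8.4.6), so it could not pass unnoticed. This part of the reply stands, and it limits the point to a rare case.

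A reader might also infer that such participants vanish from the safety data. They do not: sections 8.4.3.2 and 9.3.1 keep every exposed participant. What remains is confined to the allergic-reaction endpoints, and only if these are run on the 9.3 set. Sections 9.4.2 and 9.4.3 never name their analysis set, so that link is an inference, though a natural one, since 9.3 defines its set by follow-up for systemic allergic reaction.

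Two further inferences go too far. One is that a placebo-first participant with a short window after the vaccine counts as a non-reactor; no section says so, and the plan is silent. The other is that the bias is always downward; excluding a non-reactor raises the estimate.

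Finally, follow-up for a reaction could be read to include follow-up until the reaction occurs. That reading is possible, but the sentence specifies the initial 3 hours and makes no exception for reactors. It also does nothing for the placebo-first gap.

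**Conclusion.** The point holds as a flaw in how the analysis set is defined, with low probability and a limited scope. Section 9.3 states a completion condition that, taken literally, can exclude a vaccine-first participant with a primary event. For about half the participants that condition concerns saline, not the dose that defines the endpoint. An active dose followed by a short window has no stated handling for the primary proportion.

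With one excluded reactor and an observed rate of 20%, the estimate falls by 8.9 percentage points at N = 10 (20 - 11.1), 4.2 at N = 20 (20 - 15.8) and 0.8 at N = 100 (20 - 19.2). With one excluded non-reactor at N = 20 it rises by 1.1 points (21.1 - 20). This rests on two assumptions: that a short window occurs at all, and that the allergic-reaction endpoints use the 9.3 set. It is worth correcting because the change is small and the participants at risk of exclusion include those with the worst outcomes.

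**What to change.** Replace the definition in section 9.3 and name the set in sections 9.4.2 and 9.4.3:

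1. The primary set is all participants who receive the active injection. For the Day 1 comparison it is all who receive the first injection. Neither carries a condition on completing follow-up.
2. Any qualifying reaction observed within 3 hours of the relevant injection is an event, whether or not the 3 hours are completed.
3. A participant with a short window and no observed reaction stays in the denominator. The proportion is reported with such participants scored as non-reactors and again scored as reactors, the latter extending the missing-as-reaction imputation already in 9.4.2.

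The existing 9.4.2 provision for placebo-first participants who never receive the vaccine can stay as it is.

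The cost is a few sentences of text and one extra sensitivity line, with no new data and no change to any clinical procedure. If a short window does occur, the reported range will be slightly wider, which reflects what was not observed.
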